## 10. QUALITY CONTROL

### General database quality control

A number of open-source quality control mechanisms for the OMOP CDM have been developed (see Chapter 15 of The Book of OHDSI <http://book.ohdsi.org/DataQuality.html>). In particular, it is expected that data partners will have run the OHDSI Data Quality Dashboard tool (<https://github.com/OHDSI/DataQualityDashboard>). This tool provides numerous checks relating to the conformance, completeness and plausibility of the mapped data. Conformance focuses on checks that describe the compliance of the representation of data against internal or external formatting, relational, or computational definitions, completeness in the sense of data quality is solely focused on quantifying missingness, or the absence of data, while plausibility seeks to determine the believability or truthfulness of data values. Each of these categories has one or more subcategories and are evaluated in two contexts: validation and verification. Validation relates to how well data align with external benchmarks with expectations derived from known true standards, while verification relates to how well data conform to local knowledge, metadata descriptions, and system assumptions.

### Study specific quality control

The study code will be based on several R packages including the *CohortCharacteristics*, *CohortSurvival*, *CohortDiagnostics* and the *IncidencePrevalence* package. These packages will include numerous automated unit tests to ensure the validity of the codes, alongside software peer review and user testing. The R package will be made publicly available via the DARWIN EU® GitHub repository.

## 11. LIMITATIONS OF THE RESEARCH METHODS

### General limitations:

*Characterisation/Indication:* The ILD phenotype utilises codes recorded within databases and will not include imaging or test data. The accuracy and consistency of pre-defined condition recording, crucial for patient characterisation may vary across the databases included in the study. ILD is a complex condition and characterising the condition by subtype might be limited if ILD is only recorded as a general term without possibility to further categorise. Apart from CDWBordeaux, it is expected that some types of

	D2.2.3 - Study Protocol for P3-C1-005	
	Author(s): [name] [name]	Version: V2.1
	Dissemination level: Public	

medications related to ILD primarily administered in hospital will not be routinely captured within primary care databases. With regard to characterisation of individuals with ILD, previous exposure to smoking is of interest, however as smoking is not systematically recorded and thus not available in all databases, we have decided not to include smoking status as one of the covariates of interest. No linkage to hospitalisation diagnoses will be performed which may lead to an underestimation for certain types of covariates.

The analysis may suffer from small cell counts for some subgroup strata. If numbers are too low, counts will not be disclosed for governance reasons.

The incidence rate of ILD might be an underestimate of the actual incidence rate as ILD is a diagnosis made by the specialist. If information is not well transposed from secondary care to primary care, we might have an underestimate of the individuals with ILD.

#### Setting:

For this study, we included data from four data sources (CDW Bordeaux, BIFAP, CPRD GOLD and IQVIA DA Germany). Results of these databases may not necessarily reflect management of individuals with ILD in other countries/databases.

#### Overall survival in individuals with ILD:

As mortality is not completely documented in IQVIA Germany, this database will not be used to investigate survival in individuals with ILD.

## **12. MANAGEMENT AND REPORTING OF ADVERSE EVENTS/ADVERSE REACTIONS**

Adverse events/adverse reactions will not be collected or analysed as part of this evaluation. The nature of this non-interventional evaluation, through the use of secondary data, does not fulfil the criteria for reporting adverse events, according to module VI, VI.C.1.2.1.2 of the Good Pharmacovigilance Practices ([https://www.ema.europa.eu/en/documents/regulatory-procedural-guideline/guideline-good-pharmacovigilance-practices-gvp-module-vi-collection-management-submission-reports\\_en.pdf](https://www.ema.europa.eu/en/documents/regulatory-procedural-guideline/guideline-good-pharmacovigilance-practices-gvp-module-vi-collection-management-submission-reports_en.pdf)).

Only in case of prospective data collection, there is a need to describe the procedures for the collection, management and reporting of individual cases of adverse events/adverse reactions.

## **13. GOVERNANCE BOARD ASPECTS**

All data sources (except for IQVIA DA Germany) require approval from their respective IRB board.

## **14. PLANS FOR DISSEMINATING AND COMMUNICATING STUDY RESULTS**

A study report including an executive summary, and the specified tables and/or figures will be submitted to EMA by the DARWIN EU® CC upon completion of the study.

	D2.2.3 - Study Protocol for P3-C1-005	
	Author(s): [name] [name]	Version: V2.1
	Dissemination level: Public	

An interactive dashboard incorporating all the results (tables and figures) will be provided alongside the study report. The full set of underlying aggregated data used in the dashboard will also be made available if requested.

## 15. OTHER ASPECTS

Not applicable

## 17. ANNEXES

**Appendix I:** List of Stand-Alone documents (e.g. lists with concept definitions (conditions & drugs), validation procedures, questionnaires etc.)

Concept IDs related to ILD were identified within the Darwin Atlas and each concept ID was reviewed to decide whether it could be included as part of ILD (table S1.A) or whether it should be excluded (Table S1.B). Amongst the included concept IDs we next differentiated between alveolitis/pneumonitis, lung fibrosis, pneumoconiosis, PAP (pulmonary alveolar proteinosis) and sarcoidosis. Amongst the subclasses, 2 broad categories could be identified namely alveolitis/pneumonitis and lung fibrosis. There are some other classes too but with presumably with limited number of individuals.

**Table S1.A. Concept definitions of interstitial lung disease (ILD) and ILD-subtypes**

Concept ID	Concept Code	Concept Name	Alveolitis/ Pneumonitis	Lung fibrosis	Unspecified ILD	Drug-induced ILD*
Parents						
4197819	51615001	Fibrosis of lung		Yes		
4119786	233703007	Interstitial lung disease			Yes	
253506	205237003	Pneumonitis	Yes			
435853	10501004	Pulmonary alveolar proteinosis	Yes			
Descendants						
37312199	789574002	Acute exacerbation of idiopathic pulmonary fibrosis		Yes		
4027868	13274008	Atrophic fibrosis of lung		Yes		
4032314	14700006	Bauxite fibrosis of lung		Yes		
4275496	36599006	Chronic fibrosis of lung		Yes		
3655115	846637007	Chronic pulmonary fibrosis caused by chemical vapors		Yes		
4112681	196028003	Chronic pulmonary fibrosis due to chemical fumes		Yes		
4025168	196125002	Diffuse interstitial pulmonary fibrosis		Yes		
37017059	713244007	Drug induced pulmonary fibrosis		Yes	Yes	
4140134	426437004	Familial idiopathic pulmonary fibrosis		Yes		

Concept ID	Concept Code	Concept Name	Alveolitis/ Pneumonitis	Lung fibrosis	Unspecified ILD	Drug-induced ILD*
4197819	51615001	Fibrosis of lung		Yes		
4322799	71193007	Fibrosis of lung caused by radiation		Yes		
4066407	17385007	Graphite fibrosis of lung		Yes		
36675042	771306007	Hereditary fibrosing poikiloderma, tendon contractures, myopathy, pulmonary fibrosis syndrome		Yes		
45763750	700250006	Idiopathic pulmonary fibrosis		Yes		
600563	1017197007	Interstitial pulmonary fibrosis due to inhalation of drug		Yes		Yes
600562	1017196003	Interstitial pulmonary fibrosis due to inhalation of substance		Yes		
4236182	90610005	Interstitial pulmonary fibrosis of prematurity		Yes		
4209871	56841008	Massive fibrosis of lung		Yes		
4230447	40640008	Massive silicotic fibrosis of lung		Yes		
37208102	4.60561E+14	PF-ILD-progressive fibrosing interstitial lung disease		Yes		
253797	266368002	Post-inflammatory pulmonary fibrosis		Yes		
45769389	708030004	Pulmonary emphysema co-occurrent with fibrosis of lung		Yes		
4236725	405570007	Pulmonary fibrosis due to and following radiotherapy		Yes		
45768903	707434003	Pulmonary fibrosis due to Hermansky-Pudlak syndrome		Yes		
37109889	723829000	Pulmonary fibrosis, hepatic hyperplasia, bone marrow hypoplasia syndrome		Yes		
4025216	10613001	Acute berylliosis	Yes			
4110182	196052005	Acute drug-induced interstitial lung disorder	Yes			Yes
37312199	789574002	Acute exacerbation of idiopathic pulmonary fibrosis		Yes		
4341520	236302005	Acute interstitial pneumonia	Yes			
4112678	196021009	Acute pneumonitis due to chemical fumes	Yes			
4110644	196046009	Acute pulmonary radiation disease	Yes			
260434	196047000	Acute radiation pneumonitis	Yes			
45768986	707541006	Acute respiratory distress in newborn with surfactant disorder	Yes			
4124544	233760007	Acute silicosis	Yes			

Concept ID	Concept Code	Concept Name	Alveolitis/ Pneumonitis	Lung fibrosis	Unspecified ILD	Drug-induced ILD*
4236624	90623003	Aluminosis of lung				
4017691	115666004	Animal handlers' lung	Yes			
4142782	33548005	Anthracosilicosis		Yes		
4239466	58691003	Antimony pneumoconiosis		Yes		
256450	22607003	Asbestosis		Yes		
45768909	707443007	Autoimmune pulmonary alveolar proteinosis	Yes			
4049753	15708009	Benign pneumoconiosis		Yes		
4221139	8247009	Berylliosis	Yes			
439853	69339004	Bird-fanciers' lung	Yes			
439298	196019004	Bronchitis and pneumonitis due to chemical fumes	Yes			
4026217	12088005	Budgerigar-fanciers' disease	Yes			
4291799	37711000	Cadmium pneumonitis	Yes			
4302900	78723001	Cannabinosis	Yes			
4223637	40218008	Carbon electrode makers' pneumoconiosis		Yes		
3173010	5.92E+15	Carmustine pulmonary toxicity	Yes			
4223637	233754007	Cerium pneumoconiosis		Yes		
4232596	404807005	Cheese-washers' lung	Yes			
4119795	233728004	Cholesterol pneumonia	Yes			
4111455	18121009	Chronic berylliosis	Yes			
4112814	196053000	Chronic drug-induced interstitial lung disorders	Yes			Yes
605242	1010670004	Chronic endogenous lipoid pneumonia	Yes			
45768998	707553005	Chronic exogenous lipoid pneumonia	Yes			
762964	4.34301E+14	Chronic interstitial lung disease			Yes	
45767051	704345008	Chronic interstitial pneumonia	Yes			
45769386	708026002	Chronic pneumonitis of infancy	Yes			

Concept ID	Concept Code	Concept Name	Alveolitis/ Pneumonitis	Lung fibrosis	Unspecified ILD	Drug-induced ILD*
3655115	846637007	Chronic pulmonary fibrosis caused by chemical vapors		Yes		
4112681	196028003	Chronic pulmonary fibrosis due to chemical fumes		Yes		
37204512	783182004	Chronic respiratory distress with surfactant metabolism deficiency	Yes			
4119447	233762004	Chronic silicosis		Yes		
252946	29422001	Coal workers' pneumoconiosis		Yes		
4313425	86263001	Cobaltosis		Yes		
4040982	16623004	Coffee-workers' lung	Yes			
4216394	72270005	Collagenous pneumoconiosis		Yes		
4119442	233749003	Complicated pneumoconiosis		Yes		
4177951	49840000	Complicated silicosis		Yes		
45772936	707442002	Congenital pulmonary alveolar proteinosis	Yes			
36714118	719218000	Cryptogenic organizing pneumonia	Yes			
4120262	233692000	Cryptogenic pulmonary eosinophilia	Yes			
4311555	8549006	Desquamative interstitial pneumonia	Yes			
4028118	10713006	Diffuse interstitial rheumatoid disease of lung	Yes			
4116317	302913000	Diffuse pulmonary calcinosis		Yes		
4120270	233717003	Diffuse pulmonary neurofibromatosis		Yes		
4112813	196051003	Drug-induced interstitial lung disorder	Yes			Yes
4140472	427046006	Drug-induced pneumonitis	Yes			Yes
4177385	42680007	Endogenous lipoid pneumonia	Yes			
1340380	OMOP5166035	Exacerbation of interstitial pneumonia	Yes			
45768914	707449006	Exogenous lipoid pneumonia	Yes			
444084	37471005	Extrinsic allergic alveolitis	Yes			
4140134	426437004	Familial idiopathic pulmonary fibrosis		Yes		
435298	18690003	Farmers' lung	Yes			

Concept ID	Concept Code	Concept Name	Alveolitis/ Pneumonitis	Lung fibrosis	Unspecified ILD	Drug-induced ILD*
4002903	11944003	Feather-pickers' disease	Yes			
4249023	73448002	Fish-meal workers' lung	Yes			
4027669	13151001	Flax-dressers' disease	Yes			
4285279	68333005	Furriers' lung	Yes			
46273640	3.28641E+14	Genetic disorder of surfactant dysfunction	Yes			
4051339	233625007	Giant cell pneumonia	Yes			
4103099	192658007	GIP - Giant cell interstitial pneumonitis	Yes			
4338389	87909002	Hard metal pneumoconiosis		Yes		
42599152	3.47351E+14	Hypersensitivity pneumonitis due to inhalation of Micropolyspora faeni spores	Yes			
37110291	724499007	Idiopathic acute eosinophilic pneumonia	Yes			
37110292	724500003	Idiopathic chronic eosinophilic pneumonia	Yes			
45769390	708031000	Idiopathic eosinophilic pneumonia	Yes			
45763749	700249006	Idiopathic interstitial pneumonia	Yes			
36712839	1.2381E+13	Idiopathic pneumonia syndrome	Yes			
45763750	700250006	Idiopathic pulmonary fibrosis		Yes		
438782	40527005	Idiopathic pulmonary hemosiderosis	Yes			
4119786	233703007	Interstitial lung disease			Yes	
4140605	427123006	Interstitial lung disease due to collagen vascular disease			Yes	
46272927	711379004	Interstitial lung disease due to connective tissue disease			Yes	
42539687	737182002	Interstitial lung disease due to granulomatous disease			Yes	
3655634	866103007	Interstitial lung disease due to juvenile polymyositis			Yes	
42537658	737183007	Interstitial lung disease due to metabolic disease			Yes	
42537657	737181009	Interstitial lung disease due to systemic disease			Yes	
46270493	3.28661E+14	Interstitial lung disease of childhood			Yes	
42539090	737184001	Interstitial lung disease with systemic vasculitis			Yes	

Concept ID	Concept Code	Concept Name	Alveolitis/ Pneumonitis	Lung fibrosis	Unspecified ILD	Drug-induced ILD*
4273378	64667001	Interstitial pneumonia	Yes			
3655969	870573008	Interstitial pneumonia with autoimmune features	Yes			
600563	1017197007	Interstitial pulmonary fibrosis due to inhalation of drug		Yes		Yes
600562	1017196003	Interstitial pulmonary fibrosis due to inhalation of substance		Yes		
4218175	416916004	Lipoid pneumonitis	Yes			
4124539	233730002	Lupus pneumonia	Yes			
45768902	707433009	Lymphangioliomyomatosis due to tuberous sclerosis syndrome		Yes		
4195014	44274007	Lymphoid interstitial pneumonia	Yes			
434975	25897000	Malt-workers' lung	Yes			
4229303	88687001	Manganese pneumonitis	Yes			
438175	86638007	Maple-bark strippers' lung	Yes			
4230447	40640008	Massive silicotic fibrosis of lung		Yes		
4121294	233751004	Metal pneumoconiosis		Yes		
4119445	233758005	Mica pneumoconiosis		Yes		
4137769	32139003	Mixed dust pneumoconiosis		Yes		
4119446	233759002	Mixed mineral dust pneumoconiosis		Yes		
433233	52333004	Mushroom workers' lung	Yes			
4006973	111292008	Necrotizing sarcoid granulomatosis			Yes	
45771019	707435002	Neuroendocrine cell hyperplasia of infancy			Yes	
4121295	233755008	Nickel pneumoconiosis		Yes		
4044215	129452008	Nonspecific interstitial pneumonia	Yes			
4124537	233698001	Paprika splitters' lung	Yes			
258564	60125001	Perinatal interstitial emphysema			Yes	
37208102	4.60561E+14	PF-ILD-progressive fibrosing interstitial lung disease		Yes		
259044	40122008	Pneumoconiosis		Yes		

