##### Variables

*Condition of interest*

	D2.2.3 - Study Protocol for P3-C1-005	
	Author(s): [name] [name]	Version: V2.1
	Dissemination level: Public	

ILD and ILD-subtypes namely i) alveolitis/pneumonitis (excluding aspiration and infectious pneumonitis), ii) lung fibrosis and iii) drug induced ILD

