### Patient-level characterisation

The study cohort will include all individuals registered in the database between 1st of January 2010 and 31st of December 2022, with at least 365 days of data visibility (except for CDWBordeaux) and a new ILD diagnosis.

The concept definition of ILD and ILD-subtypes is described in Table S1, [Appendix I](#). The operational definitions of the inclusion and exclusion criteria are presented by means of [Table 5](#) and [Table 6](#), respectively.

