**D2.2.3 - Study Protocol for P3-C1-005**

**Author(s):** [name] [name]

**Version:** V2.1

**Dissemination level:** Public

Concept ID	Concept Code	Concept Name	Alveolitis/ Pneumonitis	Lung fibrosis	Unspecified ILD	Drug-induced ILD*
4093002	187233002	Sarcoidosis of lung with sarcoidosis of lymph nodes			Yes	
45771023	707510005	Secondary pulmonary alveolar proteinosis	Yes			
4050564	23315001	Sequoiosis	Yes			
4120266	233701009	Sewage workers' lung	Yes			
4144984	34004002	Siderosilicosis		Yes		
4247524	61233003	Silo-fillers' disease	Yes			
4179182	50589003	Silver polishers' lung disease	Yes			
4119441	233748006	Simple pneumoconiosis		Yes		
4243523	59773008	Simple pulmonary alveolitis	Yes			
4277596	64936001	Simple pulmonary eosinophilia	Yes			
4166078	47515009	Simple silicosis		Yes		
4124546	233767005	Stage 1 pulmonary sarcoidosis			Yes	
4124671	233768000	Stage 2 pulmonary sarcoidosis	Yes			
4119448	233769008	Stage 3 pulmonary sarcoidosis		Yes		
4119935	233770009	Stage 4 pulmonary sarcoidosis		Yes		
4196950	51277007	Stannosis		Yes		
4119444	233753001	Subacute berylliosis			Yes	
4124545	233761006	Subacute silicosis			Yes	
443890	13394002	Suberosis		Yes		
4119428	233702002	Summer-type hypersensitivity pneumonitis	Yes			
4121296	233756009	Thorium pneumoconiosis		Yes		
4119796	233733000	Toxic pneumonitis	Yes			
4027411	10785007	Vinyard sprayers' lung	Yes			
4305873	38729007	Wheat weevil disease	Yes			
4124543	233757000	Zirconium pneumoconiosis		Yes		

	D2.2.3 - Study Protocol for P3-C1-005	
	Author(s): [name] [name]	Version: V2.1
	Dissemination level: Public	

Concept ID	Concept Code	Concept Name	Alveolitis/ Pneumonitis	Lung fibrosis	Unspecified ILD	Drug-induced ILD*
1340517	OMOP5166172	Progression of massive fibrosis of lung		Yes		

PAP= Pulmonary Alveolar Proteinosis, \* Drug induced ILD can contribute to multiple categories as there are drug induced alveolitis/pneumonitis as well as drug induced pulmonary fibrosis.

	D2.2.3 - Study Protocol for P3-C1-005	
	Author(s): [name] [name]	Version: V2.1
	Dissemination level: Public	

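### Table S1.A leaves the code for drug-induced pulmonary fibrosis out of the drug-induced ILD subtype, against the table's own footnote

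*Protocol*

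**What the plan says.** The abstract names the conditions of interest as "ILD and ILD-subtypes namely i) alveolitis/pneumonitis (excluding aspiration and infectious pneumonitis), ii) lung fibrosis and iii) drug induced ILD". Section 7 and Table 1 apply these subtypes to incidence, characterisation and survival. Section 8.5 says where they are defined: "The concept definition of ILD and ILD-subtypes is described in Table S1", in Appendix I.

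Table S1.A has four flag columns: Alveolitis/Pneumonitis, Lung fibrosis, Unspecified ILD and Drug-induced ILD. The row "Drug induced pulmonary fibrosis" (37017059) has 'Yes' in the second and third and nothing in the fourth. The row "Carmustine pulmonary toxicity" (3173010) has 'Yes' in the first only. The footnote to the Drug-induced column reads "Drug induced ILD can contribute to multiple categories as there are drug induced alveolitis/pneumonitis as well as drug induced pulmonary fibrosis".

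**The concern.** A code whose name states both a drug cause and fibrosis is kept out of the drug-induced subtype and placed in the group meant for disease that is not further specified. The footnote says the opposite. Section 8.5 makes this table the operative definition, so code written from it would carry the error to every data partner. Sections 3 and 6 give signal validation for drug-induced ILD as a reason for the study, so this subtype's membership matters even though it is only one of three. The patients at stake are those whose only ILD record is 37017059. They would be absent from the subtype's incidence, medication history and survival results.

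**Working it through.** The protocol gives no figure to reproduce here. The check is a reading of rows plus two short counts.

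**Rows side by side (Table S1.A)**

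| Concept | Alveolitis/ Pneumonitis | Lung fibrosis | Unspecified ILD | Drug-induced ILD |
|---|---|---|---|---|
| 37017059 "Drug induced pulmonary fibrosis" | – | Yes | Yes | – |
| 600563 "Interstitial pulmonary fibrosis due to inhalation of drug" | – | Yes | – | Yes |
| 4140472 "Drug-induced pneumonitis" | Yes | – | – | Yes |
| 3173010 "Carmustine pulmonary toxicity" | Yes | – | – | – |

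The first two rows are the same kind of entity, fibrosis attributed to a drug, and are flagged differently. The footnote, "there are drug induced alveolitis/pneumonitis as well as drug induced pulmonary fibrosis", agrees with 600563 and not with 37017059. Row 37017059 is also the only one in Table S1.A that combines Unspecified ILD with a specific subtype. That pattern fits a mark entered one column too far to the left.

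**Count of drug-caused concepts**

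- Distinct included concepts whose name states a drug cause: 37017059, 600563, 4110182, 4112813, 4112814, 4140472, 3173010, which is 7. Concept 600563 is printed twice in the table and counted once.
- Marked Drug-induced ILD: 600563, 4110182, 4112813, 4112814, 4140472, which is 5.
- Unmarked: 7 − 5 = 2, or 2/7 = 29% of the concepts. This is a share of codes, not of patients.

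**Size of the subtype as listed (Table S2, marked codes only)**

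| Database | 4110182 | 4112813 | 4112814 | 4140472 | Sum |
|---|---|---|---|---|---|
| BIFAP | 200 | 100 | 100 | 100 | 500 |
| CDW Bordeaux | 100 | – | – | – | 100 |
| CPRD GOLD | 100 | 200 | 100 | – | 400 |
| IQVIA DA Germany | 200 | 200 | 100 | – | 500 |

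The Table 3 footnote says its counts are rounded up to the nearest hundred. I assume the same for Table S2. One person may hold several of these codes, so the sums are upper limits for the listed codes.

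Concepts 37017059, 3173010 and 600563 have no line in Table S2. That does not prove zero records, because Table S2 also lacks the parent concept 4197819 for lung fibrosis. It does mean that no patient number can be derived.

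**The case against.** **A reading artefact.** The table was read from PDF, and the main point turns on one mark in one cell. The extract has other oddities: one row (4236624) carries no flag at all, and the ID 4223637 appears against two different concepts. A shifted cell cannot be fully excluded. It is unlikely, because the row keeps all seven fields and nearby rows (600563, 4110182) show the Drug-induced mark in the right place.

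**The consequence could be read too strongly.** A reader might infer that all non-inhaled drug-induced fibrosis drops out and that the subtype reflects only pneumonitis-type reactions. The documents do not support that. Three of the five marked concepts (4112813 and its acute and chronic forms) are general by name, and nothing in those names excludes fibrosis. Only patients recorded solely under 37017059 are lost. Table S2 also shows no count in CDW Bordeaux or IQVIA DA Germany for any listed lung-fibrosis concept, so on the available counts any effect would fall in BIFAP and CPRD GOLD.

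**Carmustine.** The footnote does not name it. Concepts in Table S1.B with IDs in the same range (3168004 to 3200502) all belong to the Nebraska Lexicon, so 3173010 probably does too, and nothing shows that these European sources use it. This half rests only on the table's own pattern and stays secondary.

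**Unspecified ILD.** Table S1.A already uses this column for named conditions such as pulmonary sarcoidosis, and it is not one of the three subtypes in the objectives. One more named diagnosis there matters little. The misplaced mark is mainly evidence of the slip.

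**Centrality.** The research question in Section 7 names only the other two subtypes, and Section 8.7 puts the primary focus on ILD incidence. It would be too much to call drug-induced ILD the purpose of the study. It remains a named subtype in all three objectives.

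**Conclusion.** The point holds for 37017059: the row contradicts the footnote of its own table and the parallel row 600563. Built as listed, the drug-induced ILD cohort omits patients recorded only under that code and counts them as Unspecified ILD. For 3173010 the finding is an unexplained departure from the table's pattern, which is weaker.

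The extent is 2 of 7 distinct drug-caused concepts. The effect on patients, rates or survival cannot be derived and may be small or nil. A reader might infer from the small listed subtype (at most 100 to 500 per database on the marked codes) that the results must shift, but no count exists for either code to support that. Overall ILD is unaffected. So are the lung fibrosis and alveolitis/pneumonitis subtypes, since each code keeps its morphological mark.

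Two assumptions are made: the extracted cells match the source table, and the subtype cohorts are built from these marks row by row. Table S1.A, unlike Tables S3 and S4, has no column saying whether descendants are added, so the protocol gives no other stated route by which the unmarked codes would enter. The correction is warranted whatever the count, because the fault lies in the fixed definition of a pre-specified subtype.

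**What to change.** In Table S1.A:

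- 37017059: keep 'Yes' under Lung fibrosis and move the second 'Yes' from Unspecified ILD to Drug-induced ILD.
- 3173010: add 'Yes' under Drug-induced ILD, or add a note saying why it is left out.

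Then build the subtype cohorts from the corrected table. Concepts marked Drug-induced ILD would rise from 5 to 7, or to 6 if carmustine is left out with a reason. The cost is two cells if done before the code is released. Done later, the affected cohorts must be regenerated and the subtype analyses rerun at each data partner.
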